##### Primary Hypotheses:

1. After approximately 2-weeks of wear, the mean overall quality of vision score of the Test lenses will be statistically better than 40 points for the myope population. This will be recorded by the subject using the CLUE Follow-up Questionnaire.
2. After approximately 2-weeks of wear, the mean overall quality of vision score for the Test lenses will be statistically better than 32 points for the hyperope population. This will be recorded by the subject using the CLUE Follow-up Questionnaire.
3. After approximately 2-weeks of wear, the mean distance, binocular, high luminance, high contrast logMAR visual acuity score of the Test lens will be statistically lower than 0.10 logMAR.
4. After approximately 2-weeks of wear, the mean intermediate, binocular, high luminance, high contrast logMAR visual acuity score of the Test lens will be statistically lower than 0.17 logMAR.
5. After approximately 2-weeks of wear the mean near, binocular, high luminance, high contrast logMAR visual acuity score of the Test lens will be statistically lower than 0.17 logMAR.

**CR-6400**, Statistical Analysis Plan Version 1.0

6. When wearing the Test lenses, the proportion (%) of eyes with at least one reported clinically significant slit-lamp finding (Grade 3 or 4) during the post-fit period will be significantly lower than 5%.

7. When wearing the Test lenses, the proportion (%) of eyes with an unacceptable fit during the study will be statistically less than 5%.

If all the primary hypotheses are met, the following secondary hypothesis will be tested.

### **5.2. Secondary Hypotheses**

1. The proportion of subjects who obtain the optimum lens pair in 4 lenses or less will be at least 90% using a 95% level of confidence.

### **5.3. Other Hypotheses**

Not applicable.

## **6. ANALYSIS SETS**

### **6.1. All Enrolled**

The All Enrolled population will include all participants who sign an informed consent.

### **6.2. Intent-to-Treat (ITT)**

Intent-to-treat will include all enrolled subjects regardless of actual treatment and subsequent withdrawal from study or deviation from protocol. At least one observation should be recorded.

### **6.3. Safety Population**

All subjects who were administered any test article with at least one observation recorded excluding subjects who dropped out prior administering any test article. Safety analyses will be based on the safety population.

### **6.4. Per-Protocol (PP)**

Per Protocol Analysis set will be the primary analysis population. It will include all subjects who have successfully completed all visits and did not substantially deviate from the protocol as determined by the trial cohort review committee prior to database hard lock. Justification of excluding subjects with protocol deviations in the per-protocol population set will be documented in a memo to file.

The following is a preliminary list of criteria that may disqualify a subject from the Per-Protocol analysis. This list is simply suggestive and is subject to change at the pre-lock review:

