- Unacceptable Len Fit: The Null hypothesis will be rejected if the upper bound of the 2-sided 95% credible interval of the posterior estimate of the proportion of eyes with unacceptable lens fitting is below 5%.

If no SLF findings of Grade 3 or higher or unacceptable lens fit is observed, alternative analysis methods will be considered. More details will be provided in the statistical analysis plan.

Primary Efficacy Analyses:

Efficacy analysis will be conducted the Intent-to-Treat Population (ITT) without borrowing from historical data. A sensitivity analysis will be performed by incorporating historical historical data. The level of borrowing used in the safety analysis will be considered. Further sensitivity analyses on the Per-Protocol Population will also be considered.

CLUE Vision

CLUE vision scores will be analyzed using a Bayesian normal random effects model for repeated measures. The model will include baseline clue score, age, add power, gender, timepoint (3-day and 2-week follow-up evaluations) and strata (Hyperopes and Myopes) and the interaction between timepoint and strata as fixed effects. Site will be included as a random effect. An unstructured (UN) covariance structure will be used to model the residual errors from measurements within the same subject across timepoints. Heterogeneous residuals covariance structures (R-side) across strata will be considered when appropriate. Non-informative priors will be used for the unknown parameter. For the β coefficients, independent non-informative priors $N(0, 1000)$ will be used. For the variance of random effect σ_{site}^2 an independent non-informative conjugate prior inverse-gamma(0.001, 0.001) will be used. For the residual covariance structure an inverse-Wishart distribution will be used. Inferences will be carried out using the 95% posterior credible intervals for relevant parameters.

Hypothesis testing for CLUE Vision Scores endpoints will be conducted separately for each stratum:

- Hyperopes: The Null hypothesis will be rejected if the lower bound of the 2-sided 95% credible interval of the clue vision posterior mean estimate is above 32.
- Myopes: The Null hypothesis will be rejected if the lower bound of the 2-sided 95% credible interval of the clue vision posterior mean estimate is above 40.

Visual Acuity

Binocular high luminance, high contrast (HLHC) visual acuity (logMAR) at the 2-week follow-up evaluation will be analyzed using a Bayesian normal random-effects model for

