14.10. Procedure for Reporting Deviations from Statistical Plan

The analysis will be conducted according to that specified in above sections. There are no known reasons for which it is planned to deviate from these analysis methods. If for any reason a change is made, the change will be documented in the study report along with a justification for the change.

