## 1. INTRODUCTION

This statistical analysis plan (SAP) describes the analyses and data presentations for protocol CR-6400 Version 4.0.

This document will serve as the final guidance for all the statistical analysis for this study and will supersede the Statistical Method section in the protocol if there are any discrepancies. Any deviation from the analysis plan will be documented as such in the clinical study report.

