## 10. SUBJECT INFORMATION

### 10.1. Disposition Information

Enrolled subjects will be allocated to one of the three mutually exclusive:

1. Completed: Subjects are considered to have completed the study if they (a) provided informed consent and/or assent; (b) they are eligible; (c) completed all three phases of testing; and (d) have not withdrawn/discontinued from the study.

2. Discontinued: Subjects are considered to have discontinued from the study if (i) test article was administered and (ii) discontinued from the study. Reasons for discontinuation include: (a) Adverse Event (b) unsatisfactory visual response due to test article (c) satisfaction lens fitting due to test article (d) lens discomfort (e) lens handling difficulties (e) withdrew consent during study (f) lost to follow-up (g) subject no longer meets eligibility criteria (h) subject withdrawn by PI to non-compliance to protocol (i) test article no longer available
3. Assigned and Test Article Administered: Total number subjects for which test articles were administered (Completed + Discontinued).
4. Enrolled but Not Dispensed: Subjects are considered to be Enrolled Not Dispensed Subjects if they were (i) enrolled to the study (provided informed consent and/or assent) but failed to satisfy the eligibility criteria (inclusion/exclusion criteria) or (ii) if they are randomized but did not receive a test article.
5. Total enrolled: Completed + Discontinued + Enrolled but Not Dispensed.

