## **10.2. Protocol Deviations**

Any protocol deviation that could impact the primary endpoints will result in the subject being excluded from the Per-Protocol analysis population. No analysis on protocol deviations will be performed. All reported protocol deviations will be listed.

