### **Primary Efficacy Analyses**

Efficacy analysis will be conducted the Per-Protocol Population without borrowing from historical data. A sensitivity analysis will be performed by incorporating historical data. The level of borrowing used in the safety analysis will be considered. Further sensitivity analyses on the Safety population may also be considered if the observed subject dropout rate exceeds 15%.

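### The SAP moves primary efficacy from the protocol's ITT set to Per-Protocol without giving a reason, and so drops treated subjects with usable CLUE or VA data from a single-arm test against fixed targets

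*SAP*

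**What the plan says.** - **Protocol 14.5, Primary Efficacy Analyses:** "Efficacy analysis will be conducted the Intent-to-Treat Population (ITT) without borrowing from historical data". Per-Protocol appears there only as a further sensitivity analysis.
- **SAP 6.4:** "Per Protocol Analysis set will be the primary analysis population". SAP 11.1 accordingly runs the CLUE and VA analyses on PP. No reason is given, and the SAP's amendment history shows only the original version.
- **SAP 1:** the SAP "will supersede the Statistical Method section in the protocol if there are any discrepancies", so PP governs.
- **SAP 6.2** still defines an ITT set, but no SAP analysis is assigned to it.
- **Protocol 14.10** asks for a reason for a change, but only in the report: "If for any reason a change is made, the change will be documented in the study report along with a justification for the change".
- **Who is in PP:** subjects who completed all visits without substantial deviation (SAP 6.4). SAP 10.2 adds: "Any protocol deviation that could impact the primary endpoints will result in the subject being excluded from the Per-Protocol analysis population". Of its preliminary exclusion criteria SAP 6.4 says: "This list is simply suggestive and is subject to change at the pre-lock review".
- **The wider analysis, SAP 11.1:** "Further sensitivity analyses on the Safety population may also be considered if the observed subject dropout rate exceeds 15" per cent. No denominator is given for that rate.
- **Other provisions:** SAP 8.6 commits to a Bayesian imputation sensitivity analysis without naming a population. SAP 8.2 summarises efficacy descriptively on the Safety and PP sets.

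**The concern.** Each efficacy hypothesis compares one mean with a fixed number, so no second arm shares the effect of selection. Re-dispensing at Visit 2 requires acceptable vision, comfort and fit (Protocol 7.2, step 2.17), and failing on these grounds is a listed withdrawal reason (Protocol 8.2). Some exclusions from PP will therefore depend on how well the lens performed.

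Two groups with usable data are lost:

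- **Leavers at or after Visit 2.** They complete CLUE at Visit 2 (step 2.4). SAP 11.1 models the 3-day and 2-week scores jointly, so the 3-day score is an outcome in the primary model. They have no primary VA to lose, because logMAR visual performance is measured only at Visit 3.
- **Subjects excluded for deviations.** They may have 2-week CLUE and VA on record. Whether they would score better or worse than the rest is unknown.

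At stake is a primary set that favours the lens when leaving reflects poor vision and that is settled only at the pre-lock review. The model run that would show the effect on all treated subjects is optional.

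**Working it through.** **1. The plan's own figures.** Planning means and SDs are in Protocol Table 7 (SAP Table 5), with n = 30 per stratum for CLUE. A one-sample t-test at one-sided 0.025, which matches the rule that the 95% interval must clear the target, gives power of 99.7% for hyperopes and 99.5% for myopes. All three VA tests (n = 60, SD 0.11) exceed 99.9%. The stated 99% and >99% are reproduced.

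**2. Margins at the planning means.**

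| Test | Margin | SE | Margin / SE |
|---|---|---|---|
| CLUE hyperopes | 47.71 − 32 = 15.71 | 17.514/√30 = 3.20 | 4.9 |
| CLUE myopes | 56.46 − 40 = 16.46 | 19.227/√30 = 3.51 | 4.7 |
| VA distance | 0.10 + 0.077 = 0.177 | 0.11/√60 = 0.0142 | 12.5 |
| VA intermediate | 0.17 + 0.054 = 0.224 | 0.0142 | 15.8 |
| VA near | 0.17 − 0.077 = 0.093 | 0.0142 | 6.5 |

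**3. CLUE, vision leavers.** The documents give neither the number of leavers nor their deficit. Assume L = 1 to 3 leavers per stratum beside 30 completers, scoring 10 to 20 points lower.

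- Share lost: f = L/(30 + L), from 1/31 = 3.2% to 3/33 = 9.1%.
- Upward shift under PP: f × deficit, from 0.032 × 10 = 0.32 to 0.091 × 20 = 1.82 points.
- Pass rate with the true all-fitted mean at threshold: 1 − Φ(1.96 − shift/SE). Lowest, in myopes: 1 − Φ(1.96 − 0.32/3.51) = 3.1%. Highest, in hyperopes: 1 − Φ(1.96 − 1.82/3.20) = 8.2%. Nominal is 2.5%.
- If the 3-day scores are kept, the deficit persists from 3 days to 2 weeks and the two scores correlate at 0.5 to 0.8 (also assumed), the shift left over is f × deficit × (1 − correlation). That is 0.06 to 0.91 points, with a pass rate of 2.6% to 4.7%.

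**4. VA, deviation exclusions.** Assume k = 1 to 3 subjects with Visit 3 VA are removed, leaving 60, and that they differ from the rest by 0.10 to 0.20 logMAR.

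- Shift: k/(60 + k) × difference, from 0.10/61 = 0.0016 to 3 × 0.20/63 = 0.0095 logMAR.
- If the removed subjects are worse: 1 − Φ(1.96 − shift/0.0142) = 3.3% to 9.9%.
- If they are better: 1 − Φ(1.96 + shift/0.0142) = 1.9% down to 0.4%.
- With the direction unknown, the range is about 0.4% to 9.9%.

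**5. Would the 15% trigger fire?** Counted on treated subjects with 60 completers, 10 dropouts give 10/70 = 14.3% (no) and 11 give 11/71 = 15.5% (yes). Whole-study loss in the historical studies was 43/454 = 9.5%, ranging from 0/45 = 0% to 6/40 = 15.0%. These counts are not specific to the Test lens. The enrolment allowance is 20/80 = 25%, but it may include subjects never dispensed. Whether the trigger fires is uncertain.

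**The case against.** **The hypotheses concern about 2 weeks of wear.** Visit 2 leavers have no 2-week outcome in any population, and their 3-day score precedes optimization. Part of the dispute is therefore about which mean is wanted. This stands as a caution: the CLUE figures treat hypothetical 2-week scores as the truth, and the 3-day score may understate what those subjects could have reached. It does not explain why a score that the primary model uses for completers should be discarded for leavers.

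**Safeguards exist.** The imputation in SAP 8.6 is committed. PP subjects have completed all visits, so it would have little to do within PP and most naturally covers dropouts. The Safety-set summaries would reveal a gap between completers and all treated subjects. Both points stand, but the imputation names no population and the summaries carry no test.

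**No procedure is breached.** The protocol foresees a later SAP, the SAP claims precedence, and the reason may still come in the study report. Committee review before lock already governed PP in the protocol. The preliminary exclusion list is not visible in the text reviewed, so how open it is cannot be judged. All true, but a reason given in the report comes after the results are known.

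**Stronger readings that the documents do not support:**

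- A reader might infer that subjects discontinued at Visit 3 for fit or a Grade 3 finding fall out of PP, because the SAP's Completed category requires that they "have not withdrawn/discontinued from the study". SAP 6.4 does not refer to that category. It asks for completion of all visits, and Protocol 8.1 asks for consent, eligibility and all visits, which such subjects can meet.
- A reader might infer that the secondary test also moves to PP. SAP 11.2 names no population. The SAP overrides the protocol only where they disagree, so the ITT choice in Protocol 14.6 can stand.
- A reader might take deviation exclusions to favour the lens. Nothing in the documents says so.
- A reader might apply the 25% allowance as outcome-related loss. The documents describe it only as an enrolment margin.

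**Conclusion.** The concern holds. The SAP replaces the protocol's primary efficacy population without a stated reason. The replacement drops treated subjects with usable data from tests that have no comparator, and the all-treated model run is optional and conditional.

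The likely effect is modest. For CLUE, the PP set favours the lens to the extent that leaving reflects poor vision; the sizes in step 3 rest on assumed leaver numbers and deficits. For VA, the shift is at most 0.010 logMAR in the cases examined and could go either way. The inflated pass rates apply to a single test whose true mean sits at its threshold. All seven co-primary hypotheses must be met, so overall false success is no more likely than a false pass on any one test. The point deserves correction before database lock because it leaves open an avoidable route to bias, not because it is expected to reverse a result. The primary safety analyses stay on the Safety population and are unaffected.

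**What to change.** - **SAP 6.4 and 11.1:** return to the protocol's choice of a primary set other than PP. Define it as all subjects fitted with the Test lens who have at least one post-fit CLUE or logMAR VA value. Neither written ITT definition serves: the protocol's refers to randomized subjects in a study without randomization, and the SAP's covers all enrolled. Let early leavers' 3-day CLUE enter the existing two-timepoint model, and make PP the sensitivity analysis.
- **At minimum, if PP stays primary:** state the reason in the SAP before database lock, and make the all-fitted model run mandatory by removing both the optional wording and the 15% condition.
- **SAP 8.6:** name the all-fitted set as the population for the imputation.
- **SAP 11.2:** confirm that the secondary test stays on the protocol's non-PP population.

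The cost is SAP wording, a check that the CLUE code keeps subjects with only one of the two scores, and one extra run. The order of the two timepoints in the SAP 14.2.1 CLUE code is a separate issue to be settled on its own. The CLUE mean may be slightly less favourable, and VA for Visit 2 leavers will rest on the imputation assumptions. Power is barely affected. With completers at the planning means and 9.5% to 25% of subjects scoring 10 points lower, all-treated CLUE power is at least 99.2%; with 25% scoring 20 points lower it is about 92%.

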## 7. DEFINITIONS AND DERIVED VARIABLES

### 7.1. Age

Age will be calculated using the Date of Birth (DOB) and the date of the consenting the subject and presented as age at last birthday as an integer.

Age = Integer part of [(Date of Baseline visit – Date of Birth) / 365.25]

### 7.2. Visit Windows

Table 3: Visit window information

Scheduled Visit Number	Time Interval (label on output)	Time Interval (Day) a	Target Time Point
1	Screening	0	1
1	Baseline	0	1
2	3-Day Follow-up	2 to 4	3
3	2-Week Follow-up	10 to 14	14

a The first treatment day is Day 0.

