2.10	Lens Fit Assessment	
Evaluate and grade lens centration, primary gaze movement, upgaze movement and tightness (push-up test).
 
 • The subject should not proceed to wear the lenses if any of the following is observed: • presence of limbal exposure (appearance of clear cornea) in any gaze • presence of edge lift • presence of unacceptable movement (excessive or insufficient) in all three movement categories (primary gaze, upgaze, and push-up). 
If either lens is deemed unacceptable, the subject will be discontinued from the study. Remove the lenses, perform a slit-lamp evaluation, and complete the Final Evaluation form.
	
2.12	Lens Removal	The study lenses will be removed and discarded.	
2.13	Biomicroscopy	
Perform Biomicroscopy OD and OS. FDA Slit Lamp Classification Scales* will be used to grade the findings.
 
*note: for corneal staining note location (nasal, temporal, superior, inferior or central)
	

Clinical Study Protocol
Johnson & Johnson Vision Care, Inc.

		
If any of these slit lamp findings are Grade 3 or higher, an AE must be recorded. All AEs must be followed to resolution. After resolution the subject will be discontinued and Final evaluation completed.
 
If the clearance of the fluorescein needs to be expedited, preservative-free rewetting drops may be instilled.
	
2.14	Insertion of Study Lenses	Dispense the subject a new pair of lenses that match the distance and ADD power of the lenses that were removed in Step 2.12 above.	
2.15	PRO (MRD) Questionnaire	The subject will evaluate the vision characteristics, comfort characteristics, handling characteristics, and visual symptoms of the study lenses using the PRO questionnaire.	
2.16	Distance and Near Exit Visual Acuity	
Distance and near Snellen visual acuity will be measured for each eye with the study contact lenses in place.
 
For near measures use the ETDRS 2000 Series Chart 1 or 2.
 
The acuity will be recorded to the nearest letter OD, OS and OU.
 
Note: The distance visual acuity must be at least 20/30 OU for the lenses to be dispensed.
	
2.17	Dispensing Criteria	
The lenses will be dispensed for 10-14 days.
 
 • Distance Snellen acuity equal to or better than 20/30 OU • Subject must indicate that the vision is acceptable. • Subject must indicate that the comfort of the lenses is acceptable. • Lenses must have an acceptable general lens fit. 	

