2.18	Patient Instructions	
Instruct the Subject the following:
 
 • The lenses will be worn on a daily wear basis. • OPTI-FREE® Replenish® solution will be used in a rub regime to disinfect and store 	

Clinical Study Protocol
Johnson & Johnson Vision Care, Inc.

		
the lenses each night in the lens case provided.
 
 • If determined necessary by the Investigator sterile non-preserved rewetting drops may be dispensed to be used as needed for dryness. • Subjects will be instructed to wear lenses for a minimum of 6 hours a day, every day during the study. • Subjects will be instructed to wear their glasses when not wearing the study lenses. 
Note: In the event a lens is lost or damaged, the subject will return to the investigator site for replacement. As much as reasonably possible, a damaged lens should be returned to the investigational site and then returned to the Sponsor. If lens damage is present, complete the Product Quality Complaint Form. The lens will be stored in labeled vial with sterile saline, and returned to the Sponsor.
	
2.19	Schedule Follow-up	
The subject will be scheduled to return for their follow-up appointment in 12±2 days.
 
Note: To count the follow-up visit as a day of wear the Subject must have worn the study lenses for 6 hours prior to the visit.
	

VISIT 3

The subjects must present to Visit 3 wearing the study lenses. To be counted as a day of wear the lenses need to have been worn for at least six (6) hours prior to the visit.

Visit 3: Treatment 1 Follow-up 2		
Step	Procedure	Details
3.1	Adverse Events and Concomitant Medications Review	
Review the subject's concomitant medications and record any changes from the previous study visit.
 
Record any adverse events or medical history changes from the previous study visit.

Clinical Study Protocol
Johnson & Johnson Vision Care, Inc.

3.2	Wear time and Comfortable Wear time with Study lenses	Record the hours the subject has worn the study lenses and the comfortable wear time on the day of follow-up.	
3.3	Compliance	
Record the subject's compliance with wearing the study lenses.
 
Note: Subjects must have worn lenses for at least 6 hours per day To be counted as a day of wear at this visit the Subject must have worn the study lenses for 6 hours prior to the visit.
	

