6.0 STUDY CONDUCT DURING PANDEMIC

It is recognized that the Coronavirus Disease 2019 (COVID-19) pandemic may have an impact on the conduct of this clinical study due to, for example, self-isolation/quarantine by participants and study-site personnel; travel restrictions/limited access to public places, including Optometry Clinics; and changes in clinic procedures required to address the COVID-19 challenge.

Every effort should be made to adhere to protocol-specified assessments for study participants, including follow-up. However, if scheduled visits cannot be conducted in person at the study site it is suggested that assessments be performed to the extent possible remotely/virtually or delayed until such time that on-site visits can be resumed in order to continue participant monitoring in accordance with the protocol where possible. At each contact, participants will be interviewed to collect safety data. Key efficacy endpoint assessments should be performed if required and as feasible.

Modifications to protocol-required assessments may be permitted via COVID-19 Appendix after consultation with the participant, investigator, and the sponsor. Missed assessments/visits will be captured in the clinical trial management system for protocol deviations. Interruptions of test article wear or discontinuations of study interventions and withdrawal from the study should be documented with the prefix "COVID-19-related" in the case report form (CRF).

Title:	Guidelines for COVID-19 Risk Mitigation
Document Type:	Work Instruction
Document Number:	VWI-0081

The sponsor will continue to monitor the conduct and progress of the clinical study, and any changes will be communicated to the sites and to the health authorities according to local guidance.

If a participant has tested positive for COVID-19, the investigator should contact the sponsor's responsible medical monitor to discuss initial plans for study intervention and follow-up. The medical monitor will notify the Safety Management Team of any subject(s) that have reported "COVID-19", "Asymptomatic COVID-19", or "Suspected COVID-19" adverse events within 24 hours of the notification.

Modifications made to the study conduct as a result of the COVID-19 pandemic will be summarized in the clinical study report.

COVID-19 screening procedures that may be mandated by local healthcare systems do not need to be reported as an amendment to the protocol even if done during clinical study visits.

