### **Binocular Visual Performance**

Binocular high luminance, high contrast (HLHC) visual performance (logMAR) at the 2-week follow-up evaluation will be analyzed using a Bayesian normal random-effects model for repeated measures. The model will include strata (Hyperope and Myope), add power, age, gender as fixed effects. Site and will be included as a random effect. An unstructured (UN) covariance structure will be used to model the residual errors from measurements within the same subject across different positions. Heterogeneous residuals covariance structures (R-side) across position will be considered when appropriate.

Let  $y_{ijkl}$  denote the visual performance for the study lens for the  $j^{th}$  subject in the  $k^{th}$  strata (Hyperope or Myope), at the  $l^{th}$ site for the  $i^{th}$ position.

The Model:

$$y_{ijkl} = \mu_0 + \beta_1 age_i + \beta_2 addpwr_j + \beta_3 dist\_yn_i + \beta_4 inter\_yn_i + \beta_5 Female_j + \beta_6 Strata_k + \delta_l + \varepsilon_{ijkl}$$

- $\mu_0$ : overall intercept
- $addpwr_i$  : ADD Power
- $dist\_yn_k$  : Distance vs. Intermediate and Near
- $inter\_yn_k$ : Intermediate vs. Distance and Near
- $Female_i$  : Female indicator; Female=1 if sex='Female' and 0 otherwise
- $Strata_j$  : Strata indicator; Strata=1 if strata='Hyperope' and 0 otherwise
- $\delta_l$  : effect of the  $l^{th}$  clinical site, a random effect
- $\varepsilon_{jkl}$ : random error associated with the  $i^{th}$  position for the  $j^{th}$  subject in the  $k^{th}$  strata at the  $l^{th}$  investigational site

Here we assume  $\delta_j$  and  $\varepsilon_{jkl}$  are independent where

- $\delta_j \sim N(0, \sigma_{site}^2)$  ;
- $\begin{bmatrix} \varepsilon_{1jkl} \\ \varepsilon_{2jkl} \\ \varepsilon_{3jkl} \end{bmatrix} \sim N \left( \begin{bmatrix} 0 \\ 0 \\ 0 \end{bmatrix}, \begin{bmatrix} \sigma_{11}^2 & \sigma_{12} & \sigma_{13} \\ \sigma_{21} & \sigma_{22}^2 & \sigma_{23} \\ \sigma_{31} & \sigma_{32} & \sigma_{33}^2 \end{bmatrix} \right)$

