## 14. APPENDICES

### 14.1. Time and Event Schedule

Visit Information	Visit 1 Screening, Baseline, Treatment 1 Fitting	Visit 2 Treatment 1 Follow-up 1 Optimization	Visit 3 Treatment 1 Follow-up 2
Time Point	Day 0	Day 3±1 from V1	Day 12±2 from V2
Estimated Visit Duration	2.5 hours	1.0 hours	1.5 hours
Statement of Informed Consent	x		
Demographics	x		
Medical History/Concomitant Medications	x		
Adverse Events and Concomitant Medications Review		x	x
Compliance		x	x
Habitual Contact Lens Information	x		
Contact Lens History	x		
Wear Time and Comfortable Wear Time with Habitual Lenses	x		
Wear Time and Comfortable Wear Time with Study Lenses		x	x
Screening Inclusion/Exclusion Criteria	x		
Subject Reported Ocular Symptoms	x	x	x
Baseline Questionnaire	x		
CLDEQ-8 Questionnaire	x	x	x

Visit Information	Visit 1 Screening, Baseline, Treatment 1 Fitting	Visit 2 Treatment 1 Follow-up 1 Optimization	Visit 3 Treatment 1 Follow-up 2
Time Point	Day 0	Day 3±1 from V1	Day 12±2 from V2
Estimated Visit Duration	2.5 hours	1.0 hours	1.5 hours
Distance and Near Entrance Visual Acuity	x	x	x
Lens Removal	x	x	x
Keratometry	x		
Subjective Refraction and Distance Visual Acuity	x		
Near ADD Determination	x		
Ocular Dominance	x		
ADD Refinement	x		
Near Visual Acuity	x		
Biomicroscopy	x	x	x
Baseline Inclusion/Exclusion Criteria	x		
Eligibility	x		
Lens Selection	x	x (if modified)	
Lens Insertion	x	x	x
10 Minute Settling	x	x (if modified)	
Visual Satisfaction / Subjective Acceptance	x	x	x
Study Lens Distance and Near Visual Acuity	x	x	x
Distance Over Refraction and Visual Acuity	x	x	
Lens Fit Assessment	x	x	x
Binocular Over Refraction		x	x
Lens Deposits			x
Lens Wettability			x

Visit Information	Visit 1 Screening, Baseline, Treatment 1 Fitting	Visit 2 Treatment 1 Follow-up 1 Optimization	Visit 3 Treatment 1 Follow-up 2
Time Point	Day 0	Day 3±1 from V1	Day 12±2 from V2
Estimated Visit Duration	2.5 hours	1.0 hours	1.5 hours
Visual Performance			X
Modifications	X	X	
Post-Fit GSI Questionnaire	X	X	
Worn Lens Collection		X	X
Study Lens Questionnaire		X	X
Distance and Near Exit Visual Acuity	X	X	
Dispensing Criteria	X	X	
Instructions	X	X	
Schedule Follow-up	X	X	
Final Evaluation			X (or when subject discontinued)

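### SAP Table 3 counts the 2-week visit from Day 0, so only 6 of 15 on-schedule Visit 2/Visit 3 combinations fall inside its Day 10–14 window

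*SAP*

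**What the plan says.** SAP section 7.2, Table 3 has one column of day intervals for all visits. A footnote to that column sets the origin: "The first treatment day is Day 0". The 3-Day Follow-up (Visit 2) is Day 2 to 4, target 3. The 2-Week Follow-up (Visit 3) is Day 10 to 14, target 14. Screening and Baseline have interval 0 but target 1.

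The visit schedule is stated differently. SAP Appendix 14.1 and protocol section 7.1, Table 4 both put Visit 2 at 3±1 days from Visit 1 and Visit 3 at "Day 12±2 from V2". Protocol section 7.2 repeats this in its scheduling steps (1.33 and 2.19). At Visit 2 it adds, for the pair worn to Visit 3: "The lenses will be dispensed for 10-14 days".

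The 2-week visit carries the efficacy endpoints. For acuity, SAP section 11.1 says that "visual performance (logMAR) at the 2-week follow-up evaluation will be analyzed", and SAP section 5.1 sets both CLUE hypotheses after about two weeks of wear.

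**The concern.** A window table in the SAP's definitions section is there to be programmed, and this one carries the output labels. Read as written, its 2-week row does not describe the visit that the protocol schedules. A subject seen exactly on plan falls outside the window, while its first two days belong to no on-schedule visit.

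The row is the time point of five of the seven co-primary hypotheses: CLUE vision in myopes and in hyperopes, and acuity at distance, intermediate and near. SAP sections 6.4 and 11.1 make Per-Protocol the primary efficacy population, and SAP section 10.2 excludes subjects whose deviations could affect a primary endpoint. A window that marks compliant visits as out of range is a poor input to that review, even if every case is later resolved correctly.

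**Working it through.** **Inputs.** Visit 2 on Day 2, 3 or 4 (3±1 from Visit 1) and Visit 3 at 10, 11, 12, 13 or 14 days after Visit 2 (12±2): SAP Appendix 14.1 and protocol Table 4. Window Day 10 to 14, target 14, origin Day 0: SAP Table 3.

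**Reproducing Table 3.** The Visit 2 row follows from the schedule: 3−1 = 2 and 3+1 = 4, target 3. The Visit 3 range follows only if counted from Visit 2: 12−2 = 10 and 12+2 = 14.

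**Visit 3 counted from Day 0.** Study day = Visit 2 day + interval. Earliest 2+10 = 12, latest 4+14 = 18, nominal 3+12 = 15. There are 3 × 5 = 15 combinations.

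| Visit 2 on | On-schedule Visit 3 days | Inside Day 10–14 | Count |
|---|---|---|---|
| Day 2 | 12, 13, 14, 15, 16 | 12, 13, 14 | 3 |
| Day 3 | 13, 14, 15, 16, 17 | 13, 14 | 2 |
| Day 4 | 14, 15, 16, 17, 18 | 14 | 1 |

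The total inside is 3+2+1 = 6 of 15. As distinct study days, 3 of the 7 possible days (12, 13, 14 out of 12 to 18) fit. Days 10 and 11 never occur on schedule.

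**By interval since Visit 2.** 10 days: 3 of 3 inside. 11 days: 2 of 3. 12 days (nominal): 1 of 3. 13 and 14 days: 0 of 3 each.

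**Could another origin rescue the row?** Day 1 is tried because the Screening and Baseline targets are 1.

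| Origin | On-schedule range | Combinations in 10–14 | Nominal day against target 14 |
|---|---|---|---|
| Day 0 (the footnote) | 12–18 | 6 of 15 | 15 |
| Visit 1 as Day 1 | 13–19 | 3 of 15 | 16 |
| Visit 2 | 10–14 | 15 of 15 | 12 |

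No single origin makes footnote, range and target all correct.

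**Checking the two repairs.** Counted from Visit 2, 10–14 days with target 12 fits 15 of 15. Counted from Day 0, Day 12–18 with target 15 also fits 15 of 15, but it is looser. It admits 3 × 7 = 21 pairings of Visit 2 day and Visit 3 day, of which 21−15 = 6 are off schedule, with intervals from 12−4 = 8 to 18−2 = 16 days.

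**The case against.** The strongest reply is that this is a labelling slip with no effect on the analysis. The range is evidently 12±2 carried over from Visit 2. The right schedule is in the same SAP, and the SAP supersedes only the protocol's statistical section (SAP section 1), so the visit schedule stands. The table is keyed by scheduled visit number, and the visible analysis works the same way. SAP section 8.2 removes only unscheduled visits from the efficacy analysis, and the CLUE code in SAP Appendix 14.2.1 takes two follow-up scores with no day variable. On the visible text a scheduled Visit 3 on Day 15 is analysed.

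Most of that stands, and it limits the consequence. It does not make the row right: even on the charitable origin, the target is the upper limit of the range rather than its centre, and the footnote is false for that row.

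Three stronger readings are tempting, and the documents do not support them.

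- A reader might infer that on-time primary-endpoint data will be excluded. No visible rule drops or reassigns data by study day. A trial cohort review committee decides Per-Protocol status, and the SAP section 6.4 list of possible disqualifiers is not in the available text.
- A reader might infer that the window licenses visits that are too early, with a pair worn for fewer than 10 days. Such visits already breach the protocol schedule, and Table 3 does not authorise them.
- A reader might link this to protocol Appendix I, section 6.0, which lets "assessments be performed to the extent possible remotely/virtually or delayed until such time that on-site visits can be resumed", and infer that a delayed subject is left without a stop day for a two-week lens. That cannot be concluded. The Patient Instruction Guide and part of Appendix I are not in the available text. The visible text also sets two-week replacement, a dispensing period, remote checks of wear compliance, and recording of wear interruptions.

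**Conclusion.** The 2-week row of SAP Table 3 is wrong as written. Under its own stated origin it contains 6 of 15 on-schedule combinations and misses the nominal visit by one day (Day 15 against an upper limit of 14). Under the Visit 2 origin the range is right, but the target is two days too late (14 against 12).

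This is a minor error at an important time point. The risk that the documents support is that compliant Visit 3 dates are flagged as out of window when the table is programmed or when Per-Protocol status is reviewed. No bias or loss of subjects can be shown.

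The count assumes whole-day visits and takes the footnote literally. The 15 combinations are not equally likely, and 6 of 15 is not a forecast share of subjects. The documents contain no actual visit dates, so the number of subjects affected cannot be estimated.

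**What to change.** Correct the 2-week row of SAP Table 3 in one of two ways.

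1. Preferred: count the row from the Visit 2 dispensing date, 10 to 14 days, target 12, and have the footnote say that this row uses that origin. This matches the protocol schedule exactly.
2. Keep the Day 0 origin for the whole table and state Day 12 to 18, target 15. This keeps a single origin but accepts the few off-schedule pairings shown above.

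The same edit could bring the Screening and Baseline targets (1) into line with their interval (0).

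The cost is one table row and one footnote. Protocol section 15.2 already requires visit dates and dispensing records to be kept, so no new data, visits or analyses are needed. The visit schedule does not change.
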